7.11 Product Accountability

Product accountability is not required since the Medtronic SynchroMed II infusion system and PFMS used in this study are commercially available. All devices and drugs used during the study will be purchased by sites through their standard procedure for acquiring commercial product and maintained per the applicable product labeling and the institutions' standard procedures.

8. Study Site Requirements

All investigator and site selection activities were complete prior to implementation of CIP V3.0.

8.1 Investigator/Investigation Site Selection

All investigators managing the subject's chronic pain must be qualified practitioners and experienced in the diagnosis and treatment of subjects with chronic pain. All PIs or appropriately delegated Sub-Investigators must be experienced and/or trained in the implant and management of the Medtronic SynchroMed II infusion system.

The role of the principal investigator is to implement and manage the day-to-day conduct of the clinical investigation as well as ensure data integrity and the rights, safety and well-being of the subjects involved in the clinical investigation.

The principal investigator shall:

- Be qualified by education, training, and experience to assume responsibility for the proper conduct of the clinical investigation
- Be experienced in the field of application and training in the use of the Medtronic SynchroMed II infusion system

- Disclose potential conflicts of interest, including financial, that interfere with the conduct of the clinical investigation or interpretation of results
- Be able to demonstrate that the proposed investigational study site:
 - Has the required number of eligible subjects needed within the recruitment period
 - Has one or more qualified investigators, a qualified investigational study site team and adequate facilities for the foreseen duration of the clinical investigation

Study site personnel training will be completed and documented prior to participation in this study.

8.2 Study Site Activation

During the activation process (prior to subject enrollment), Medtronic will train study site personnel according to their delegated tasks and in accordance with the study training plan. If new members join the study site team, they will receive training on the applicable study requirements relevant to their role before contributing to the study.

Prior to performing study related activities, all regulatory requirements shall be fulfilled, including, but not limited to the following:

- IRB approval of CIP and site-specific ICF
- Fully executed Clinical Trial Agreement
- Financial disclosure
- Curriculum Vitae of investigators and key members of the investigation study site team
- Documentation of delegated tasks
- Documentation of study training
- Additional requirements imposed by the IRB shall be followed, if appropriate.

Medtronic will provide each study site with documentation of study site/investigator readiness; this letter must be received prior to performing study related activities.

9. Selection of Subjects

9.1 Study Population

Patients with chronic, intractable, non-malignant primary back pain with or without leg pain, are the intended study population.

9.2 Subject Enrollment

93 subjects with chronic, intractable, non-malignant primary back pain with or without leg pain that met eligibility criteria and provided written informed consent/HIPAA were enrolled in this study. Subjects were enrolled at 16 study sites in the US, with no more than 15 subjects enrolled at each site, unless the site received pre-approval from Medtronic for additional enrollments.

9.3 Inclusion Criteria

A potential subject may be included for participation in the study if the subject has/is:

1. Willing and able to provide a signed and dated (Medtronic and Institutional Review Board (IRB) approved) Informed Consent Form (ICF) and Health Insurance Portability and Accountability Act (HIPAA) Authorization Form prior to any study procedures being performed
2. A candidate per labeling for the IDDS
3. A diagnosis of chronic, intractable, non-malignant primary back pain with or without leg pain, treatable with the IDDS
4. Current daily systemic opioid dose of >0 and ≤ 120 Morphine Milligram Equivalents (MME)
5. A Visual Analogue Scale (VAS) of ≥50 mm for pain intensity at the Baseline Visit and/or a Numerical Opioid Side Effect (NOSE) Assessment Tool ≥40 for intolerable side effects at the Baseline Visit
6. Psychological evaluation or investigator assessment of patient psychological suitability for study participation
7. Has an MRI or CT prior to enrollment verifying patent spinal canal and no clinical change in status since last imaging
8. At least 18 years old at time of enrollment
9. Willing and able to attend visits and comply with the study protocol
10. Male or non-pregnant, non-lactating female. Females must be post-menopausal or surgically sterile; or be utilizing a medically acceptable form of birth control (i.e. a hormonal contraceptive, intra-uterine device, diaphragm with spermicide, or condom with spermicide) for the duration of the study

9.4 Exclusion Criteria

A potential subject will be excluded from participating in the study if the subject has/is:

1. Previously trialed or implanted with an IDDS
2. Concomitant stimulation device implanted for the treatment of pain
3. Any ongoing health condition that would be expected to interfere with pain and/or quality of life ratings (i.e. active malignancy, other painful conditions not treatable with IT therapy, etc.)
4. Psychological or other health conditions, financial and/or legal concerns that would interfere with the subject's ability to fulfill the requirements of the protocol as per the investigator's discretion

5. Substance Use Disorder (SUD) within the last 2 years or current Medication Assisted Treatment (MAT) for substance use disorder
6. Currently using cannabinoids or illicit drugs
7. History of allergy or significant adverse reaction to morphine per investigator discretion
8. Currently participating or plans to participate in another investigational study unless written approval is provided by Medtronic Study Team

10. Study Procedures

10.1 Summary of Visits

Study procedures and data collection requirements for the study are provided in detail below for each visit and summarized in Table 3: Schedule of Events within Section 10.11. Refer to Section 6, Figure 1: Embrace TDD Study Visit Flowchart for a diagram of the required study visits.

A summary of the required visits are as follows:

- Baseline Visit
- Intrathecal Trial Visit
- Implant Visit
- Post-Op Visit
- 1-Month Visit
- 3-Month Visit
- 6-Month (Study Exit) Visit

Table 2: Visit Windows provides details regarding the study visit windows for all required study visits.

Table 2: Visit Windows

Study Visits	Visit Windows	
Baseline Visit	Date of Enrollment (Date ICF/HIPAA signed and dated)	
Intrathecal Trial Visit	After Baseline and prior to Implant	
IT Therapy Initiation (Day 0) Implant to Post-Op Visit	Implant Visit	≤ 150 days after the Baseline Visit
	Post-Op Visit	14 ± 4 days after the Implant Visit
	1-Month Visit	30 days ± 5 days after Day 0
	3-Month Visit	90 days ± 10 days after Day 0
	6-Month Visit (Study Exit)	180 days ± 10 days after Day 0

10.2 Baseline Visit

Subjects are considered enrolled at the time the study-specific informed consent/HIPAA form is signed. At the Baseline Visit, the Medtronic and site Institutional Review Board (IRB) approved informed consent/HIPAA form will be reviewed with the potential subject. If the subject agrees to participate, they will be consented and assessed for eligibility to the study-specific inclusion and exclusion criteria. Each subject must meet all the inclusion criteria and none of the exclusion criteria to be eligible to participate in this study. No study-related procedures or testing will be conducted prior to completing the consenting process of a subject.

Subjects will be asked to complete the VAS for pain intensity and the NOSE assessment tool. Site personnel will confirm the subject's VAS score ≥ 50 mm or the subject's NOSE score ≥ 40 to be eligible to continue in the study. Female subjects of child-bearing potential (not post-menopausal or surgically sterile) must be administered a urine pregnancy test to confirm they are not pregnant at this visit. A subject who has a positive urine pregnancy test will be exited from the study according to Section 10.10. In addition, site personnel must confirm the drug testing results are negative for cannabinoids and illicit drugs for all subjects. If subjects meet all the eligibility criteria, their chronic back (and leg, if applicable) pain history and surgical history will be collected and the study investigator will discuss the process for weaning off systemic opioids with the subject.

Systemic Opioid Weaning and Holiday

Investigators should begin weaning the subject off their systemic opioids on the day of their Baseline Visit (i.e., enrolment date). The method of the opioid weaning process is at the investigator's discretion, but must be completed within the following constraints:

- Total duration (Baseline to Implant \leq 5 months)
- Systemic opioid dose of \leq 60 MME before IT trial
- Minimum opioid holiday of at least 7 days prior to IT Therapy Initiation

If a subject has been enrolled in the study and is determined to be ineligible during the Baseline Visit, or they choose to withdraw early, the subject will be exited according to Section 10.10.

Data Collection Requirements for the Baseline Visit:

- ICF/HIPAA
- Inclusion/exclusion criteria
- VAS
- NOSE
- Demographics
- Back (and leg, if present) pain history/surgical history
- Adjunctive pain management therapies utilized
- Urine pregnancy test results, if applicable
- Drug testing for systemic opioids, cannabinoids, and illicit drug use

[REDACTED]

- Pain medications
- AEs

10.3 Intrathecal Trial Visit

Site personnel must ensure the subject meets eligibility criteria prior to initiating any IT drug trial procedures. Subjects will be asked to complete the VAS for pain intensity and the NOSE assessment tool. The investigator must then confirm the subject's systemic opioid dose is \leq 60 MME prior to moving forward with the IT drug trial. Females of child-bearing potential (not post-menopausal or surgically sterile) must be administered a urine pregnancy test at this visit to confirm they are not pregnant. In addition, site personnel must confirm each subject's drug testing results for systemic opioids and confirm results are negative for cannabinoids and illicit drugs. If it is determined the subject no longer meets eligibility criteria, or they choose to withdraw early, the subject will be exited from the study according to Section 10.10.

The IT trial will be conducted according to the investigator's standard of care procedures. A successful IT trial will be determined by the investigator and documented accordingly.

If the investigator determines the IT trial was not successful, the subject will be considered a screen failure and will be exited from the study according to Section 10.10.

Data Collection Requirements for the IT Trial Visit:

- Inclusion/exclusion criteria
- VAS
- NOSE
- Adjunctive pain management therapies utilized
- Urine pregnancy test results, if applicable
- Drug testing results for systemic opioids, cannabinoids, and illicit drugs
- Date systemic opioids were stopped, if prior to trial
- IT trial method, drug name, lot number/identifier, dose(s) and concentration(s)
- Pain medications
- AEs

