10.10 Study Exit

Normal study completion occurs when the subject has completed the required study visits through the 6-Month Visit (refer to required procedures described in Section 10.7), at which time the subject will end their participation in the study and site personnel will then complete required eCRFs. If a subject has already completed their 6-Month visit, they will be brought into re-consent, and be exited from the

study. If the subject is an early withdrawal, refer to Section 10.21 for subject withdrawal or discontinuation procedures.

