10.21 Subject Withdrawal or Discontinuation

A subject has the right to withdraw from the study at any time and for any reason without prejudice to his/her future medical care by the PI or institution. Subjects will be provided standard medical care by their physician after their study participation ends.

The study sample size accounts for potential attrition. Therefore, subjects that discontinue after enrollment in the study will not be replaced.

If a subject is withdrawn from the study, the reason for withdrawal shall be recorded on a study exit eCRF and in the subject's medical record.

Examples of reasons for study discontinuation include, but are not limited to, the following:

- Eligibility criteria not met (prior to implant)
- Pregnancy
- Subject death
- Subject lost to follow-up (LTFU)
- Subject voluntarily withdraws from the study
- Adverse events
- Normal study completion

A study exit eCRF must be completed for any enrolled subject who permanently discontinues from the study regardless of whether they discontinue early or complete the protocol-required study follow-up and has completed the study.

Study site personnel must make a minimum of three attempts to contact a subject before a subject can be considered LTFU for this study. Site personnel must document those attempts and the method of attempt (e.g. two by phone and one by certified letter) to contact the subject in the subject's medical and/or study records. In addition, any other requirements set forth by the governing IRB must be followed.

The investigator should make all attempts to conduct an in-office discontinuation visit prior to subject withdrawal if the subject is withdrawn after the device is implanted. All eCRFs should be completed for visits that occurred prior to the subject's withdrawal. In addition, regardless of when the discontinuation occurs, site personnel should request an update on the status of any medications, ongoing adverse event or device deficiency. If a subject discontinues prior to completing the 6-Month Visit, site personnel should request the subject complete all applicable subject assessments required at the 6-Month Visit, if the subject is willing, to ensure final assessments for the study are obtained whenever possible.

11. Risks and Benefits

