11.1 Potential Risks

The SynchroMed II infusion system, which includes a SynchroMed II implantable pump, implantable catheters, accessory kits, and clinician and patient therapy applications, is commercially available in the United States. The risks associated with the products and procedures are no different than those for SynchroMed II infusion system patients outside of this clinical study. Risks are disclosed in the device labeling included with each product. Refer to the appropriate device labeling for all current risks, contraindications, warnings and precautions. Risks associated with the use of PFMS are no different for subjects participating in this study than they are for patients who receive PFMS outside of this clinical study. Risks are disclosed in the drug labeling included with the product. Refer to the appropriate drug labeling for all current risks, contraindications, warnings, precautions, dosage and administration information and screening procedures. As such there is no incremental risk associated with the participation in the Embrace TDD Clinical Study.

Systemic Opioid Weaning Risks:

Investigators must review risks associated with systemic opioid weaning with each study subject. Opioid withdrawal symptoms may vary depending on each's subjects current regimen of systemic opioids, and the method(s) utilized to assist with the weaning may impact any associated risks. Examples of withdrawal symptoms may include, but are not limited to the following:

- Headache
- Muscle aches, restlessness
- Anxiety
- Insomnia
- Diarrhea
- Nausea and vomiting
- Rapid heartbeat

Risks associated with Implantation or Use of an infusion system:

- Pocket seroma, hematoma, erosion, or infection
- Infection
- Pump inversion (“flipping”)
- Placement of the catheter may expose patients to risks of postlumbar puncture (spinal headache), cerebral spinal fluid (CSF) leak and CSF subcutaneous collection or rare central nervous system (CNS) pressure-related problems, radiculitis, arachnoiditis, bleeding, spinal cord damage, or meningitis
- Inflammatory mass could result in neurological impairment, including paralysis

- Allergic or immune system response to the implanted materials. A listing of device materials can be found in the Device Specifications sections of the implant manuals for the pump and catheters

System- and Procedure-Related Complications:

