Malfunction: (ISO 14155:2011 3.27)	
Failure of an investigational medical device to perform in accordance with its intended purpose when used in accordance with the instructions for use or (CIP).

Use Error: (ISO 14155:2011 3.43)	
Act or omission of an act that results in a different medical device response than intended by the manufacturer or expected by the user.
 
NOTE 1: Use error includes slips, lapses, and mistakes.
 
NOTE 2: An unexpected physiological response of the subject does not in itself constitute a use error.

Term	Seriousness
Serious Adverse Event (SAE): (ISO 14155:2011 3.37)	
Adverse event that
 
 a) led to death, b) led to serious deterioration in the health of the subject, that either resulted in 
 1) a life-threatening illness or injury, or 2) a permanent impairment of a body structure or a body function, or 3) in-patient or prolonged hospitalization, or 4) medical or surgical intervention to prevent life-threatening illness or injury or permanent impairment to a body structure or a body function, c) led to fetal distress, fetal death or a congenital abnormality or birth defect. 
NOTE: Planned hospitalization for a pre-existing condition, or a procedure required by the CIP, without serious deterioration in health, is not considered a serious adverse event.

Term	Definition
Serious Adverse Device Effect (SADE): (ISO 14155:2011 3.36)	Adverse device effect that has resulted in any of the consequences characteristic of a serious adverse event
Term	Relatedness
Systemic Opioid Weaning-Related	An adverse event related to the systemic opioid weaning process (i.e. opioid-related withdrawal symptoms)
Device-Related	An adverse event that results from the presence or performance (intended or otherwise) of the SynchroMed II infusion system.
IT Drug-Related	Event related to the IT drug delivered by the device. Normally IT drug-related events resolve when the device is turned off or reprogrammed, or the drug is removed from the pump. This category should not include events that resulted from a malfunction of the device (i.e. hardware-related events).
Procedure-Related	An adverse event that occurs due to any procedure related to the IT trial, implant, pump refills, programming, or surgical modification of the system.

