12.2 Reporting of Adverse Events

Any AE meeting the definition of systemic opioid weaning-related, device-related (i.e. SynchroMed II infusion system), IT drug-related, and procedure-related (i.e. IT trial, implant or pump refill/reprogramming, system modification), and all serious adverse events and deaths (regardless of relatedness), for all subjects from the Baseline Visit through study exit will be collected.

It is the responsibility of the investigator to identify the occurrence of any reportable adverse events and to ensure all required information is accurately recorded in the subject's medical record and reported to Medtronic on an event eCRF. IRB reporting must be completed in accordance with the policies of the governing IRB. Refer to the eCRF for the information to be reported for each AE.

For AEs that require immediate reporting, initial reporting to Medtronic may be done by phone, fax, or e-mail, or on the eCRF by completing as much information as is available. The AE eCRF must be completed as soon as possible.

In case the investigator requires information from the sponsor in an emergency, the investigator can contact Medtronic using the contact details provided in the synopsis and Section 12.5.

The clinical course of each AE must be followed until the adverse event is resolved, the subject is in a stable condition, or until the subject discontinues from the study. "Ongoing" AEs must be assessed at each study visit. The AE eCRF should be updated when there is a change to the information provided on the form (e.g. change in intervention, outcome, relatedness, etc.).

At the last study visit, the investigator will instruct the subject to provide an update on the status of any ongoing events and report any AE they believe may be related to participation in the study.

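### Subjects whose intrathecal trial fails are exited without a timed safety contact after the procedure, and the SAP places procedure-related events in an analysis set that leaves them out

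*Protocol*

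**What the plan says.** **Exit after a failed IT trial.** Under Protocol 10.3, if the investigator judges the IT trial unsuccessful, "the subject will be considered a screen failure and will be exited from the study according to Section 10.10". Section 10.10 contains no safety step of its own: "If the subject is an early withdrawal, refer to Section 10.21 for subject withdrawal or discontinuation procedures".

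**What 10.21 asks for.** The investigator should try to "conduct an in-office discontinuation visit prior to subject withdrawal if the subject is withdrawn after the device is implanted". A trial failure has no implant, so this visit does not apply. A weaker step covers every exit: "regardless of when the discontinuation occurs, site personnel should request an update on the status of any medications, ongoing adverse event or device deficiency". It has no timing.

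**AE window.** Under Protocol 12.2, reportable AEs "for all subjects from the Baseline Visit through study exit will be collected". Follow-up of a known AE may also stop when the subject discontinues. At the last study visit the investigator tells the subject to report AEs thought to be related to taking part. AEs are also collected at the IT Trial Visit itself (10.3).

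**Scope.** Table 4 in Protocol 12.1 defines a procedure-related event as "An adverse event that occurs due to any procedure related to the IT trial, implant, pump refills, programming, or surgical modification of the system". The safety objective covers all subjects from enrollment to exit. Among the risks of implanting or using an infusion system, Protocol 11.1 says: "Placement of the catheter may expose patients to risks of postlumbar puncture (spinal headache), cerebral spinal fluid (CSF) leak".

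**Analysis sets.** SAP 7.1.3 names the Full Analysis Set (all enrolled) for safety. It also names the Implanted Analysis Set for AEs related to device, IT drug and procedure. It defines an IT Trial Analysis Set but gives it no use in the visible text.

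**The concern.** A complication of the IT trial need not be present when the subject leaves the trial visit. A trial success goes on to further visits at which AEs are collected, so a late event can still be recorded. A trial failure can be exited at once, and an event that appears afterwards falls outside the collection window. Completeness of capture would then depend on the outcome of the IT trial.

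The subjects affected are those who were exposed to the procedure and the trial drug and did not go on to therapy. If their late events are missed while they stay in the denominator, the risk of the IT trial comes out too low. The SAP wording adds a separate problem: even an event that was recorded in a trial failure may be left out of the procedure-related table, if that table is built on implanted subjects.

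**Working it through.** **1. Contacts after the procedure, by outcome of the IT trial**

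| Step | Trial success, then implant | Trial failure |
|---|---|---|
| AE collection at the IT Trial Visit (10.3) | yes | yes |
| AE collection at Implant, Post-Op, therapy initiation, months 1, 3 and 6 (10.4 to 10.7, Table 3) | yes | none |
| In-office discontinuation visit (10.21) | asked for if withdrawn after implant | not asked for |
| Status update at exit (10.21) | yes | yes, untimed, worded for ongoing events |
| Instruction at last study visit (12.2) | normally month 6 | may be the IT Trial Visit itself |

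For a failure, nothing in the right-hand column has to happen later than the day of the procedure.

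**2. The plan's attrition figures, which bound the number of failures**

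Inputs are from Protocol 14.1.1 and SAP section 6: 33% lost before implant, 25% lost from implant to month 6.

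- 100 × (1 − 0.33) = 67.0 implanted
- 67 × (1 − 0.25) = 50.25 evaluable

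The planned chain of 100, 67 and 50 reproduces. With 93 enrolled and the intended 67 implanted, 93 − 67 = 26 are not implanted. Failed IT trials are only one of several listed reasons for pre-implant loss, so 26 is an upper bound on failures.

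**3. Share of late events lost**

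Let F be the number of failures and RR the risk of a late event in failures relative to successes. Assume 67 successes, every late event in failures missed, and all trialled subjects in the denominator. Then

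share lost = F × RR / (67 + F × RR)

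| F | RR = 1 | RR = 2 |
|---|---|---|
| 5 | 5/72 = 6.9% | 10/77 = 13.0% |
| 10 | 10/77 = 13.0% | 20/87 = 23.0% |
| 20 | 20/87 = 23.0% | 40/107 = 37.4% |
| 26 (bound) | 26/93 = 28.0% | 52/119 = 43.7% |

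For example, at RR = 1 a true late risk of 10% would be seen as 6.7/72 = 9.3% with F = 5, and as 6.7/93 = 7.2% with F = 26. F and RR are assumptions; the documents give neither.

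**4. Effect of the denominator**

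If the table uses implanted subjects only, failures leave both numerator and denominator. At RR = 1 the late-event rate is then unbiased. At RR = 2 it falls short of the rate in all trialled subjects by 1 − (67 + F)/(67 + 2F):

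- F = 5: 1 − 72/77 = 6.5%
- F = 26: 1 − 93/119 = 21.8%

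So the direction and size depend on which of the two sets in SAP 7.1.3 is used, and the SAP does not settle that.

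**The case against.** **Safety contacts do exist.** A reader might infer that trial failures get no safety contact at all. The documents do not support that. AEs are collected at the trial visit, 10.21 asks for a status update at any exit, and the instruction in 12.2 is not limited to ongoing events. This stands, and it narrows the point to timing. These steps reduce the gap but do not close it, because none has to come after the period in which a late event could appear.

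**Bias is not shown.** A reader might also infer that IT-trial risk is in fact understated. The number of failures, the time from trial to exit and the late-event rates are all absent, and nothing says that exit takes place on the trial day. This stands: the loss is a possibility, not a result.

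**No separate IT-trial rate is planned in the visible text.** Table 4 puts the IT trial together with implant, refill, programming and modification, and SAP 7.10 tabulates by that category. This is true, and it is a reason to add the table. Part of the SAP after 7.9.4 is blacked out, so a use of the IT Trial Analysis Set there cannot be ruled out.

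**The named risks may not carry over.** Spinal headache and CSF leak are listed for implantation or use of the system, while the IT trial method follows the investigator's own practice. Their relevance therefore varies by method. The point does not rest on them, since Table 4 makes any IT-trial event reportable.

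**The sums need care.** Taking 33% of 93 gives 30.7 pre-implant exits, but that goes with 93 × 0.67 = 62.3 implanted and cannot be set beside 67. Equating 67 implanted with 67 trial successes is also an assumption, because SAP 7.1.1 expects some exits due to COVID-19 or pump supply.

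**Little can still change in conduct.** Enrollment is closed at 93 and implant is due within 150 days of Baseline, so few trial failures, perhaps none, are still to be exited. This stands, and it puts the weight on the SAP.

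**Conclusion.** The concern holds in a limited form. After a failed IT trial no safety contact is tied to a time after the procedure, AE collection ends at exit, and late-onset events may be captured less completely in failures than in successes. Separately, SAP 7.1.3 names two different sets for procedure-related and IT drug-related AEs. One of them leaves out trial failures, although the safety objective covers all subjects.

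Under the equal-risk assumptions in the working, the share of late events lost runs from 7% to 23% for 5 to 20 failures, with a ceiling of 28% if all 26 non-implanted subjects were failures. These are worst-case shares for each F at equal risk, because every late event in failures is taken as missed; the true share could be near zero. Doubling the risk in failures raises the range for 5 to 26 failures to 13% to 44%. The primary endpoint is not affected. The point is worth acting on because the reporting part is cheap and does not depend on the unknown event rates.

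**What to change.** **SAP 7.1.3 and 7.10.** State which set is used for device-, IT drug- and procedure-related AEs, so that the two statements no longer conflict. Report IT-trial procedure-related and drug-related AEs in the IT Trial Analysis Set, split by trial outcome, with days from trial to exit for each group. Short follow-up in failures is then visible to the reader, including for those already exited. The cost is one extra table from AEs and dates that should already be recorded.

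**Protocol 10.3 and 10.21, for any trial failures not yet exited.** Make the existing status update a documented contact that takes place after the procedure and before the exit eCRF is completed, and have it ask for new as well as ongoing events. The sponsor should set the interval. The 14 ± 4 days in the Protocol belongs to the post-implant visit and is not stated for the IT trial. The cost is a short delay of exit for the few subjects concerned, and a protocol amendment with IRB approval if these sections are edited.
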